6.1.3.1 Hospitalizations, Health Economic, and Quality of Life Variables

Health economics and clinical outcomes research variables include the following. Further analyses of these endpoints will be described in a separate SAP.

- Subjects' quality of life variables
 - EuroQol (EQ-5D) dimensions
 - Mobility
 - Self-Care
 - Usual Activities
 - Pain/Discomfort
 - Anxiety/Depression
 - Functional Assessment of Cancer Therapy – Bone Marrow Transplant (FACT-BMT)
 - Work Productivity and Activity Impairment Questionnaire: General Health (WPAI: GH)
- Health Economic Assessment (HEA)

The EQ-5D, FACT-BMT and WPAI: GH are assessed at each dosing visit, at V13 and at the Primary Study Period Completion/Day 365 Visit (V14). Information about administration of these assessments can be found in the study protocol.

Health economic information will be collected for subjects through the Primary Study Period Completion/Day 365 Visit (Visit 14).

6.1.3.1.1 Health Economic Assessments

Health Economic Assessments will include the following: concomitant medications and procedures, hospitalizations, nonscheduled clinic visits and emergency room visits. The information will be collected by the site via a retrospective review of the subject's medical record. HEA data will include both data being routinely captured for the subject (e.g., concomitant medications) as well as data that will be used specifically for these analyses (e.g., information on hospitalizations).

6.1.3.1.2 EuroQol (EQ-5D)

The EQ-5D is an international standardized non-disease-specific (i.e., generic) instrument for describing and valuing health status. It is a measure of health-related quality of life (QOL), capable of being expressed as a single index value and specifically designed to complement other health status measures. The EQ-5D has 5 dimensions: Mobility, Self-Care, Usual Activities, Pain/Discomfort and Anxiety/Depression. Each dimension has 5 response levels (e.g., 1=no problems, 2=slight problems, 3=moderate problems, 4=severe problems,

5=extreme problems). In addition, it has a visual analogue scale that elicits a self-rating by the respondent of his/her health status.

6.1.3.1.3 Functional Assessment of Cancer Therapy-Bone Marrow Transplant (FACT-BMT)

The Functional Assessment of Cancer Therapy-Bone Marrow Transplant (FACT-BMT) is a self-administered instrument designed to assess multi-dimensional aspects of QOL in bone marrow transplant (BMT) patients. It consists of the 27-item FACT-General (FACT-G) and the 23-item Bone Marrow Transplantation Subscale (BMTS). The FACT-G assesses 4 primary dimensions of QOL, including physical well-being (7 items), social-family well-being (7 items), emotional well-being (6 items) and functional well-being (7 items). A 5-point response scale ranging from 0 to 4 is used (0 = 'not at all'; 1 = 'a little bit'; 2 = 'somewhat'; 3 = 'quite a bit'; and 4 = 'very much').

6.1.3.1.4 Work Productivity and Activity Impairment Questionnaire: General Health (WPAI: GH)

The Work Productivity and Activity Impairment Questionnaire: General Health (WPAI: GH) is a 6-question instrument designed to assess the effect of health problems (physical or emotional problem or symptom) on an individual's ability to work and perform regular activities [see Protocol Appendix 16]. The WPAI: GH is assessed at each dosing visit, at V13 and at the Primary Study Period Completion/Day 365 Visit (V14).

Questions of the WPAI: GH are as follows.

1. Are you currently employed (working for pay)?
2. During the past 7 days, how many hours did you miss from work because of your health problems? *Include hours you missed on sick days, times you went in late, left early, etc., because of your health problems. Do not include time you missed to participate in this study.*
3. During the past 7 days, how many hours did you miss from work because of any other reason, such as vacation, holidays, time off to participate in this study?
4. During the past 7 days, how many hours did you actually work?
5. During the past 7 days, how much did your health problems affect your productivity while you were working?

Think about days you were limited in the amount or kind of work you could do, days you accomplished less than you would like, or days you could not do your work as carefully as usual. If health problems affected your work only a little, choose a low number. Choose a high number if health problems affected your work a great deal.

6. During the past 7 days, how much did your health problems affect your ability to do your regular daily activities, other than work at a job?

By regular activities, we mean the usual activities you do, such as work around the house, shopping, childcare, exercising, studying, etc. Think about times you were limited in the

amount or kind of activities you could do and times you accomplished less than you would like. If health problems affected your activities only a little, choose a low number. Choose a high number if health problems affected your activities a great deal.

If the answer to Question 1 is “No”, Questions 2 through 5 are skipped. The answers to Questions 2, 3, and 4 are given in hours. If the answer to Question 4 is “No”, Questions 5 is skipped. Question 5 is answered by circling a number from 0 to 10, with 0 representing “Health problems had no effect on my work” and 10 representing “Health problems completely prevented me from working”. Question 6 is likewise answered by circling a number from 0 to 10, with 0 representing “Health problems had no effect on my daily activities” and 10 representing “Health problems completely prevented me from doing my daily activities”.

WPAI: GH outcomes are expressed as impairment percentages, with higher numbers indicating worse outcomes, as follows.

Q1 = currently employed.

Q2 = hours missed due to health problems.

Q3 = hours missed other reasons.

Q4 = hours actually worked.

Q5 = degree health affected productivity while working.

Q6 = degree health affected regular activities.

If Q1 = ‘Yes’ then the following are calculated.

Percent work time missed due to health = $100\% \times Q2/(Q2+Q4)$.

Percent impairment while working due to health = $100\% \times Q5/10$.

Percent overall work impairment due to health

$$= 100\% \times Q2/(Q2+Q4) + [(1 - (Q2/(Q2+Q4))) \times (Q5/10)].$$

If Q1 = ‘No’ then the above quantities should be considered missing values.

For all subjects, the following will be calculated.

Percent activity impairment due to health = $100\% \times Q6/10$.

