The EQ-5D response for each domain will be summarized by treatment arm at each visit. The total FACT-BMT and the corresponding change from baseline will be summarized by treatment arm at each visit and at final visit. The productivity outcomes from the WPAI will be summarized by treatment arm at each visit and at final visit. Treatments will be compared with respect to these scales using analysis of covariance of change from baseline to final visit with treatment, donor-recipient relatedness, and donor CMV serostatus as factors and baseline value as a covariate.

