- If the month and year of the onset date is on or after the month and year of the first dose of study drug, then the imputed onset date will be the **latest** of the following non-missing dates:
 - Date of first dose of study drug
 - Surrogate onset date

If the imputed onset date is after the adverse event end date, the imputed onset date will be the same as the adverse event end date.

No imputation of missing data for other variables will be done.

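### The WPAI overall work impairment formula in the SAP applies 100% to only one of its two terms and has no rule for employed subjects who worked zero hours

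*SAP*

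**What the plan says.** SAP 6.1.3.1.4 states that "WPAI: GH outcomes are expressed as impairment percentages, with higher numbers indicating worse outcomes". For employed subjects it defines three work scores:

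- percent work time missed: 100% x Q2/(Q2+Q4);
- percent impairment while working: 100% x Q5/10;
- "Percent overall work impairment due to health": 100% x Q2/(Q2+Q4), plus a square-bracketed term (1 - Q2/(Q2+Q4)) x Q5/10. The bracket closes around the second term only.

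If the subject is not employed, "then the above quantities should be considered missing values". No rule covers an employed subject with zero hours worked. On skipping, the SAP says that if Q4 is answered No, "Questions 5 is skipped", although the same paragraph says that Q4 is answered in hours. The questionnaire in protocol Appendix 16 sends the subject past Q5 when Q4 is 0. SAP 7.10.1 ends with "No imputation of missing data for other variables will be done".

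On analysis, protocol 7.4.3 states: "The productivity outcomes from the WPAI will be summarized by treatment arm at each visit and at final visit". It then compares treatments by ANCOVA, as does the synopsis. SAP 7.4.3.2 summarises and tests one WPAI score only, percent activity impairment, which comes from Q6. SAP 6.1.3.1 leaves further analyses of these variables to a separate SAP.

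**The concern.** The overall score combines two parts: time lost from work, and reduced productivity during the time worked. If 100% scales only the first part, a 0-100 quantity is added to a 0-1 quantity and the on-the-job part almost vanishes. Subjects who work full hours while badly impaired would look nearly unimpaired.

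The second gap concerns employed subjects who missed all their hours for health reasons. Q5 is blank for them, so the printed expression multiplies zero by a blank. If that is evaluated directly, subjects at the top of the impairment scale have no overall score. This pattern is foreseeable, because the WPAI is collected at each dosing visit, V13 and V14 in the year after transplant.

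What is at stake is the correctness and reproducibility of one exploratory derived score.

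**Working it through.** The SAP gives no worked example, so there is no figure to reproduce. The check evaluates the formula directly, using the definitions in SAP 6.1.3.1.4 and the skip rule in protocol Appendix 16.

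Let A = Q2/(Q2+Q4).

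- As printed, with 100% used as a multiplier as in the two sibling scores: P = 100 x A + (1 - A) x Q5/10.
- With both terms scaled: B = 100 x [A + (1 - A) x Q5/10].
- Shortfall: B - P = (100 - 1) x (1 - A) x Q5/10 = 99 x (1 - A) x Q5/10. It is largest at A = 0 and Q5 = 10, where it is 99 points.

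| Q2 | Q4 | Q5 | A | P (as printed) | B (both scaled) | B - P |
|---|---|---|---|---|---|---|
| 10 | 30 | 5 | 0.25 | 25 + 0.75 x 0.5 = 25.375 | 100 x (0.25 + 0.375) = 62.5 | 37.125 |
| 20 | 20 | 5 | 0.5 | 50 + 0.5 x 0.5 = 50.25 | 100 x (0.5 + 0.25) = 75 | 24.75 |
| 0 | 40 | 10 | 0 | 0 + 1 x 1 = 1 | 100 | 99 |
| 4 | 36 | 0 | 0.1 | 10 + 0 = 10 | 10 | 0 |

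The last two rows show the mis-ordering. A subject who works full hours but is completely impaired scores 1, below the 10 of a subject who missed 4 of 40 hours and was otherwise unimpaired. With both terms scaled the values are 100 and 10.

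Alternative reading, with 100% as the number 1: for Q2=20, Q4=20, Q5=5 the printed expression is 0.5 + 0.5 x 0.5 = 0.75, which is the right value as a fraction.

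Zero hours worked, employed:

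- Q2=40, Q4=0, Q5 skipped. A = 1, so the second term is 0 x (blank). SAP 7.1 specifies SAS, where a product with a missing factor is missing, so the score comes out missing. Algebraically the weight on Q5 is 1 - A = 0, so B = 100 for any Q5. Percent work time missed is still 100, and percent activity impairment is still available from Q6.
- Q2=0, Q4=0. A = 0/0, so the overall score and percent work time missed are both undefined. This pattern does not indicate high impairment, since all the hours may have been missed for other reasons.

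**The case against.** Four points can be made against this.

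1. Strictly, 100% equals 1, and the printed expression is then correct. A reader might infer from the table that the formula is simply wrong. The documents do not go that far: the text is wrong under one reading and right under another. The sibling formulas favour the first, because a multiplier of 1 would have no purpose in them. The ambiguity stands, and one outer bracket removes it.

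2. The missing score is an inference. A reader might conclude that the SAP excludes the most impaired subjects. It gives no such instruction and is silent on the case. The result follows from the Q5 skip, the no-imputation sentence and SAS arithmetic. Assigning 100% when Q2 > 0 is derivation, not clearly imputation. Those subjects also keep two other WPAI scores, and the documents do not say how many there would be. This objection limits the claim but does not remove the need for a rule.

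3. A reader might suppose that a planned treatment comparison is distorted. Within this SAP none is: SAP 7.4.3.2 uses only the Q6 score, whose formula is sound and which is calculated for all subjects. This objection stands in full and sets the size of the point.

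4. The protocol speaks of productivity outcomes without naming them, so it does not by itself require this score to be reported. That is also correct. What remains is a mismatch between protocol and SAP to be reconciled.

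**Conclusion.** The point holds as a defect in a written derivation, with low impact. If 100% is used as it is in the sibling formulas, the overall score is understated by 99 x (1 - A) x Q5/10 points, by at most 99, and subjects can be ranked wrongly. For employed subjects with no hours worked the SAP gives no rule. If Q2 > 0 and the formula is evaluated directly in SAS, a score that should be 100% is lost.

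Both conclusions rest on stated assumptions: the scaling reading of 100%, and literal coding of the expression with Q5 blank. The primary and secondary endpoints and the activity impairment analysis are untouched. The error would matter if the productivity outcomes planned in protocol 7.4.3 and the synopsis are reported, or if the separate SAP carries the derivation over.

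**What to change.** In SAP 6.1.3.1.4:

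- Write the score as 100% x {Q2/(Q2+Q4) + [1 - Q2/(Q2+Q4)] x Q5/10}.
- Set it to 100% when Q1 = Yes, Q2 > 0 and Q4 = 0.
- Set it to missing when Q2 + Q4 = 0, and say that percent work time missed is then missing too.
- Change the trigger for skipping Q5 from an answer of No to 0 hours, to match protocol Appendix 16.

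In SAP 7.4.3.2, state which WPAI outcomes are reported there and which are left to the separate SAP, so that it agrees with protocol 7.4.3 and the synopsis.

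The derivation changes cost a few lines of text and code, with no new data. Reconciling the reported outcomes is a separate decision, and costs one sentence if the work scores are deferred. SAP section 1 already provides for analytical changes after the final version to be documented in the study report.

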6.1.4 Immunogenicity Variables

An indicator of immunogenicity elicited by the vaccine is expected to be an increase in Gb-specific antibody levels and the T-cell response to the pp65 protein over time compared with the placebo group.

Two immunogenicity assessments will be performed:

1. T-cell response to viral protein pp65 using cultured ELISpot .
2. Antibody response to gB antigen using an ELISA-based platform.

Assessments will be done from peripheral blood mononuclear cells (T-cells) or serum samples (antibody) isolated over the course of the trial. Time points of the assessments are as follows:

On Visits V2, V5, V8, V9 and V11 and V14:

- Samples for T-cell assays will not be collected if the Absolute Lymphocyte Count (ALC) is known to be $\leq 500 \text{ mm}^3$ by local or central laboratory measurement.
- If the visit coincides with a study drug administration, the sample will be drawn prior to injection.

Further details will be available in the Laboratory Manual.

6.2 Safety Variables

Safety will be assessed by evaluation of the following variables:

- Vital signs (systolic and diastolic blood pressure, pulse rate, respiratory rate, temperature and weight).
- Adverse events using the NCI-CTCAE v. 4.03 grading scale.
- Acute and non-acute Local reactogenicity signs and symptoms using the protocol-specified reactogenicity scales, as described in Appendix 7 of the study protocol.
- Clinical laboratory assessments.
- Physical examinations.
- Treatment emergent adverse events (TEAEs; frequency, severity, seriousness and relationship to study drug).

Per protocol, All AEs and SAEs will be collected from signing of the ICF through 30 days post last dose of study drug. All events requiring adjudication, Grade 3 and higher AEs and SAEs will be collected from 31 days post last dose of drug through 1 year post-transplant. TEAE is defined as an adverse event observed on the day or after the first injection up to 1 year post-transplant. If the adverse event occurs on the day of the first injection of study drug and the onset check box is marked "Onset after first dose of study drug" or the onset check box is left blank in eCRF, then the adverse event will be considered treatment emergent. If the adverse event occurs on the day of the first injection of study drug and the onset check box is marked "Onset before first dose of study drug", then the adverse event will not be considered treatment emergent. If a subject experiences an event both during the pre-investigational period and during the investigational period, the event will be considered as TEAE only if it has worsened in severity (i.e., it is reported with a new start date).

The definition of TEAE for this SAP includes adverse events through 1 year post-transplant, regardless of the date of last study medication, rather than only 30 days after the last dose of study medication. This is because, as noted above, all events requiring adjudication, Grade 3 and higher AEs and SAEs are collected through 1 year post-transplant. A drug-related TEAE is defined as any TEAE with possible or probable relationship to study treatment as assessed by the investigator. Any AE with a missing relationship per the investigator will be counted as study drug related AE in the summary.

Any AE with a missing severity per the investigator will be counted as severe, and any AE with a missing seriousness per the investigator will be counted as serious.

Astellas 'Always Serious AE' are identified by Astellas and then queries are issued to the Investigator to consider upgrading the event to serious. If the investigator agrees to upgrade, then the site submits an SAE form for the event and adds the SAE number to RAVE. If they do not agree to upgrade the event, then only the SAE number is entered into RAVE. If an AE has an SAE number on RAVE it is considered Serious even if not indicated as such on the AE record.

6.3 Pharmacokinetic Variables

Pharmacokinetics will not be analyzed in this study.

6.4 Pharmacodynamic Variables

Pharmacodynamics will not be analyzed in this study.

7 STATISTICAL METHODOLOGY

7.1 General Considerations

All statistical analyses and summary information will be generated according to this statistical analysis plan. Any analytical deviations from this plan will be documented in the clinical study report. All numerical rounding should be performed at the end of calculations. The p-values will be displayed with 3 significant digits. Statistical significance will be determined prior to rounding the p-value.

For continuous variables, descriptive statistics will include the number of subjects (n), mean, standard deviation (SD), median, minimum and maximum. Frequencies and percentages will be displayed for categorical data. Percentages by categories will be based on the number of subjects with no missing data (i.e., will add up to 100%).

The analyses with the randomization stratification factors, donor-recipient relatedness (Related/Non-related) and donor CMV serostatus (Positive/Negative), that are used in the analyses will be based on the data from IRT.

All statistical comparisons will be made using 2-sided tests at the $\alpha=0.05$ significance level unless specifically stated otherwise.

The analysis day will be calculated from the day of transplantation day (efficacy analysis day 0). Further details on data handling conventions are specified in Section [7.10](#) For patients who took study drug but did not receive HCT, the analysis day will be calculated from the first study drug injection day (safety analysis day 1).

This SAP includes the plan for data analysis for the primary study period (i.e., 1-year post transplantation) which is defined as data collected through day 380 (=365+14+1 day) from transplantation. The long-term follow-up period is not covered by this SAP and will be managed in a separate SAP.

All data processing, summarization, and analyses will be performed using SAS[®] Version 9.4 or higher on Unix.

7.2 Study Population

7.2.1 Disposition of Subjects

Disposition of subjects will be summarized for the following:

- Number and percentage of subjects with informed consent, discontinued before randomization, and randomized (overall only);
- Number and percentage of subjects randomized in each analysis set, by treatment group and overall;
- Number and percentage of subjects completed and discontinued treatment, by reason for treatment discontinuation for randomized subjects, by treatment group;
- Number and percentage of subjects completed and discontinued the study, by reason for study discontinuation for randomized subjects and by treatment group;
- Number and percentage of subjects excluded from the PPS by reason for exclusion defined in Section 5.3.1 by treatment group for the FAS and mFAS

Number of subjects randomized in each country and site will be tabulated by treatment group and overall.

7.2.2 Protocol Deviations

Protocol deviations as defined in the study protocol (Section 8.1.6 Protocol Deviations) will be assessed for all randomized subjects. The number and percentage of subjects meeting the criteria will be summarized for each criterion and overall, by treatment group and total as well as by study site. Subjects deviating from a criterion more than once will be counted once for the corresponding criterion. Subjects who meet more than 1 criterion will be counted once in the overall summary. A data listing will be provided by site and subject.

The unique protocol deviation criterion will be as follows:

- PD1 - Entered into the study even though they did not satisfy entry criteria,
- PD2 - Developed withdrawal criteria during the study and was not withdrawn,
- PD3 - Received wrong treatment or incorrect dose,
- PD4 - Received excluded concomitant treatment.

7.2.3 Demographic and Other Baseline Characteristics

Demographic and other baseline characteristics will be summarized descriptively by the treatment group and overall for FAS, mFAS, PPS-FAS, PPS-mFAS, SAF, mSAF, and xSAF populations.

Descriptive statistics for age, weight, body mass index (BMI) and height at study entry will be presented. Frequency tabulations for sex, ethnicity, age group (Age < 65 years, Age ≥ 65 years), race, BMI categories (<25, 25 to <30, and ≥30 kg/m²), ATG use, AML use, and myeloablative conditioning regimen will be done. Randomization strata donor-recipient

relatedness and donor CMV serostatus will be tabulated. Each of these combinations will also be tabulated. The ATG use (Yes/NO) and myeloablative or nonmyeloablative conditioning regimen will be tabulated from the eCRF according to the investigator's assessment.

Medical history is coded in MedDRA and will be summarized for treatment group and overall for SAF. One summary table will include SOC and PT and the other summary table will include PT in descending order of total group.

7.2.4 Previous and Concomitant Medications

Previous and concomitant medications are coded with WHO-DRL, and will be summarized by therapeutic subgroup (ATC 2nd level) and chemical subgroup (ATC 4th level) and preferred WHO name by treatment group for the FAS and mFAS populations.

Previous medications are defined as medications that patients started and ended prior to first administration of study medication. Concomitant medications are defined as any medications that patients took after the first dose of study medication and through 1-year post-transplantation (i.e., 380 days from transplantation). Any previous medications that continued while study drug was given will be counted as both previous and concomitant medications.

Subjects taking the same medication multiple times will be counted once per medication and investigational period. A medication which can be classified into several chemical and/or therapeutic subgroups is presented in all chemical and therapeutic subgroups.

Antiviral therapies, including those used for reasons other than CMV infection, are of special interest. These medications will be summarized by reason for use.

